The research question in the primary aim 1 will be addressed by comparing the CPAP adherence at post-intervention among the three intervention groups (UC, SM, SM-Mobile) and secondary aims 2 and 3 will be addressed by comparing the three intervention groups (UC, SM, SM-Mobile) on the changes in PACIC, OSA symptoms and OSA HRQOL from pre-intervention to post-intervention. The analytic model is based on an analysis of variance on the post-intervention measure (primary aim) or the change measures (secondary aims). For the change measures, the ANOVA will be accompanied by an analysis of covariance (ANCOVA) on the change scores with intervention as a main effect and the corresponding baseline measurement (baseline PACIC, OSA symptoms and OSA HRQOL) as the covariate. Adjustments will be made to correct for other baseline imbalances between groups, and to adjust for variables known to influence outcome independently of intervention. To explore this, univariate methods will be used. Each of the following variables will be assessed for imbalance between the three intervention groups and their association with each of the outcomes using a univariate analysis (ANOVA, Fisher's exact test or Spearman correlation coefficient as appropriate): age, gender, education and baseline OSA

severity. These variables will be included as covariates in the ANCOVA model if found to be moderately associated ($p < 0.15$) with the outcome under study (CPAP adherence, CAHPS, PACIC, OSA symptoms and OSA HRQOL) or unbalanced ($p < 0.10$) among intervention groups. The outcomes in secondary aims 2 and 3 will also be assessed by the random effects model, which is useful for examining changes in variables from clustered or longitudinal data and allows us to account for all levels of clustering when analyzing the data. It accommodates unequal time intervals and will include all available data, minimizing the effects of missing data on the analyses. The data analytic plan for secondary aim 4, which involves a cost analysis among three interventions [and a calculation of the adherence level per intervention cost], is fully described in section D.7 below. An intent-to-treat analysis will be performed and no correction will be made for multiple comparisons. All above analyses will be performed in R.¹¹⁰ Given below are detailed analysis plans for the primary aim and secondary aims 1 and 2.

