Aim 1: An ANOVA will be used to assess the CPAP adherence at post-intervention among the three groups. Followed will be an ANCOVA by including potential covariates. Any variable that is significantly different at baseline ($p < 0.10$) and found to be associated with response ($p < 0.15$) as well as any clinically significant variables will be included as covariates.

Aim 2: An ANOVA will be used to assess the post vs. pre changes in PACIC among the three groups. An ANCOVA will be performed with treatment as a main effect and baseline score as a covariate. Any variable that is significantly different at baseline ($p < 0.10$) and found to be associated with response ($p < 0.15$) as well as any clinically significant variables will be included as covariates. As a secondary analysis, the change in PACIC will also be evaluated using a random effects model with a group, time and a group-by-time interaction term.

Aim 3: An ANOVA will be used to assess the post vs. pre changes in OSA symptoms and OSA HRQOL among the three groups. An ANCOVA will be performed with treatment as a main effect and baseline score as a covariate. Any variable that is significantly different at baseline ($p < 0.10$) and found to be associated with response ($p < 0.15$) as well as any clinically significant variables will be included as covariates. As a secondary analysis, a random effects model with a group-by-visit interaction term will be used to assess the rate of change in PACIC differs among three intervention groups.

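### For Aims 2 and 3 the SAP bases the analysis on an unadjusted change-score ANOVA, runs the baseline-adjusted ANCOVA beside it, and does not say which decides

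*Combined protocol and SAP*

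**What the plan says.** The Data Analytic Plan in the SAP sets the general model: "The analytic model is based on an analysis of variance on the post-intervention measure (primary aim) or the change measures (secondary aims"). It goes on: "For the change measures, the ANOVA will be accompanied by an analysis of covariance (ANCOVA) on the change scores". That second model compares the arms after adjusting for each outcome's own starting value, which the SAP describes thus: "the corresponding baseline measurement (baseline PACIC, OSA symptoms and OSA HRQOL) as the covariate".

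The aim-by-aim text keeps that order. Under Aim 2: "An ANOVA will be used to assess the post vs. pre changes in PACIC among the three groups". Under Aim 3: "An ANOVA will be used to assess the post vs. pre changes in OSA symptoms and OSA HRQOL among the three groups". Each is followed by the same sentence: "An ANCOVA will be performed with treatment as a main effect and baseline score as a covariate".

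A third model is planned and, unlike the other two, is given a rank. For Aim 2: "As a secondary analysis, the change in PACIC will also be evaluated using a random effects model". The Aim 3 paragraph likewise labels its random effects model secondary.

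On multiplicity the Data Analytic Plan says: "An intent-to-treat analysis will be performed and no correction will be made for multiple comparisons". Nothing in the SAP says whether the ANOVA or the ANCOVA settles a secondary outcome, or what follows if they disagree.

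**The concern.** Two tests of the same hypothesis are planned for every change outcome, and the text gives the leading place to the one that ignores the baseline value. Two things are at stake.

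- **Precision.** Subtracting the baseline score removes its influence with a fixed slope of 1. ANCOVA estimates the slope from the data. Unless the true slope happens to be 1, the change score carries avoidable noise, and confidence intervals for the arm differences are wider than they need to be.
- **Pre-specification.** With no named deciding test and no multiplicity correction, a positive result can be claimed from whichever p-value is smaller. The error rate of that procedure is above the nominal level of either test.

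The issue is confined to the secondary aims. The primary adherence outcome is analysed as a post-intervention value, not as a change.

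**Working it through.** **Inputs.** The SAP states no sample size, power, target difference, arm size or baseline/follow-up correlation, so there is no design figure to reproduce. No secondary outcome has both a baseline and a follow-up SD:

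- ESS has a baseline SD of 5.3 (Finding, Overall Sample) and no follow-up SD.
- PACIC has one SD of 1.1 per arm (Finding, Aim 2) and no baseline value.
- PSQI has means only (Finding, Aim 3).

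Everything below therefore uses assumed values of rho, the baseline/follow-up correlation, and k, the follow-up SD divided by the baseline SD.

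**Step 1: residual variances**, in units of the baseline variance.

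- Change-score ANOVA: 1 + k² − 2·rho·k
- ANCOVA on baseline: k²·(1 − rho²)
- Difference: 1 − 2·rho·k + rho²·k² = (1 − rho·k)²

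The difference is a square, so in large samples the ANCOVA is never less precise. The two are equal when rho = 1/k.

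**Step 2: equal SDs (k = 1).** The ratio ANCOVA/change is (1 − rho²) / [2(1 − rho)] = (1 + rho)/2.

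| rho | Change | ANCOVA | Ratio |
|---|---|---|---|
| 0.3 | 1.40 | 0.91 | 0.65 |
| 0.5 | 1.00 | 0.75 | 0.75 |
| 0.7 | 0.60 | 0.51 | 0.85 |

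**Step 3: unequal SDs.** At rho 0.3, 0.5 and 0.7 the ratio is 0.502, 0.571 and 0.628 for k = 0.8, and 0.762, 0.871 and 0.966 for k = 1.2. Over rho from 0.2 to 0.9 and these values of k the extremes are:

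- k = 0.8, rho = 0.2: 0.6144 / 1.32 = 0.47
- k = 1.2, rho = 0.8: 0.5184 / 0.52 = 0.997

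The gain therefore ranges from more than half the variance to almost nothing.

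**Step 4: the same ratio as patient numbers.** This is illustrative only: one pairwise comparison, an assumed difference of 0.5 baseline SD, two-sided 5%, 80% power, k = 1. Patients per arm, change score v ANCOVA, are 88 v 58 (rho 0.3), 63 v 48 (0.5) and 38 v 33 (0.7). At the larger number in each pair, ANCOVA has about 93.5%, 90% and 86% power.

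**Step 5: using either p-value.** Simulation under the null: three equal arms, normal data, k = 1, each test at 5%, 20,000 trials per setting.

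| Per arm | rho | Either test significant | Tests disagree |
|---|---|---|---|
| 50 | 0.3 | 7.8% | 5.5% |
| 50 | 0.5 | 7.2% | 4.8% |
| 50 | 0.7 | 6.5% | 3.4% |
| 80 | 0.3 | 8.2% | 6.0% |
| 80 | 0.5 | 7.2% | 4.7% |
| 80 | 0.7 | 7.1% | 3.8% |

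Each test alone rejected in 4.7% to 5.3% of trials. At a rate near 7%, the simulation standard error is √(0.07 × 0.93 / 20,000) = 0.18 percentage points.

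**The case against.** The strongest reply is that the recommended model is already in the plan. That is correct, and it sets the limit of this point. A reader might infer that baseline adjustment was left out; it was not. Precision is lost only where the ANOVA is the result relied on. What remains is that the plan names the ANOVA as its basis, gives the ANCOVA an accompanying role and ranks neither against the other, although it does rank the random effects model.

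Four further inferences are tempting and are not supported.

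- **That the change-score ANOVA is biased** because it lets regression to the mean into the comparison. Over randomisation both tests are unbiased. A chance baseline imbalance affects the unadjusted estimate in a given trial, but that is part of its larger variance.
- **That change scores are noisier at every correlation below 1.** This holds for equal SDs. With k = 1.2 the excess vanishes at rho = 1/1.2 = 0.83, and nothing in the documents establishes equal SDs.
- **That a specific loss of power can be attached to this trial.** That would need an arm size, a target difference and a correlation, none of which is given. The planned test also compares three groups, whereas Step 4 is pairwise.
- **That the reported findings are selective.** The PACIC total, ESS and PSQI comparisons are all stated as showing no group difference, and the widest 4-month ESS gap is 8.2 − 7.4 = 0.8 points. No positive claim appears that a choice between tests could have produced.

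The null results do not make the point moot. The findings for these outcomes give group means without naming the test or giving an adjusted difference or interval, so a reader cannot tell which planned analysis lies behind them.

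**Conclusion.** The point stands for Aims 2 and 3 only, as one of efficiency and pre-specification. The SAP rests the change outcomes on the test that is never the more precise in large samples, and leaves it unranked against the better one. Where the ANOVA is relied on, the ANCOVA would have 65% to 85% of its residual variance if SDs are equal and rho lies between 0.3 and 0.7; if SDs differ, the saving may be larger or almost nil. Where either p-value may be used, the per-outcome false-positive rate is about 6.5% to 8%, assuming equal SDs, rho 0.3 to 0.7 and 50 to 80 patients per arm. The direction of the precision result follows from the algebra; its size in this trial cannot be computed from the documents.

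**What to change.** State in the SAP that the single deciding analysis for PACIC, OSA symptoms and OSA HRQOL is the ANCOVA on arm plus the outcome's own baseline value. Follow-up score or change may serve as the dependent variable; once baseline is in the model, the arm effect is the same. Make the change-score ANOVA descriptive support and keep the random effects model as the labelled secondary analysis. The rule for adding further covariates is a separate question and need not be settled for this change.

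Because results are already reported, new wording alone is not enough. Report the baseline-adjusted arm differences with confidence intervals, say which test produced the comparisons now stated, and disclose that the ranking was set after the results were known.

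The model is already planned and uses the baseline scores that the plan itself calls for, so no new data are needed. The cost is a short SAP revision, a small amount of reporting, and accepting that the ranking is post hoc.

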Overall Sample: The overall sample was aged 53.1 ± 13.6 , had a body mass index (BMI) of 32.6 ± 5.7 , apnea-hypopnea index (AHI) of 30.3 ± 18.9 , and a baseline Epworth Sleepiness Score (ESS) of 11.8 ± 5.3 . 90% of the sample were men. There were no significant differences between the groups on BMI, AHI, ESS, sleep apnea symptoms, insomnia symptoms or depressive symptoms.

Aim 1: To examine the effect of the Self-Management Care delivered by mHealth (SM-Mobile) intervention compared to Usual Care (UC) and Self-Management Care (SM) on level of CPAP adherence relative to Usual Care. The three groups were compared to see if there were differences on adherence. No statistically significant differences were found between UC, SM and SM-Mobile groups at the 2-month timepoint (4.0 ± 2.2 , 3.9 ± 2.4 , and 3.8 ± 2.4 hours per night, respectively; $F = .113$; $p = .893$). or the 4-month timepoint (3.6 ± 2.2 , 3.6 ± 2.5 , and 3.6 ± 2.5 hours per night, respectively; $F = .041$; $p = .959$).

In addition, we had CPAP efficacy metrics, including the residual Apnea-Hypopnea Index (AHI) and mask leak. At the 4-month time point, CPAP resulted in very good control of sleep apnea as evidenced by the mean AHI of 3.3 across the entire group. There were no group differences on residual AHI (UC, SM, and SM-Mobile of 3.0, 3.6 and 3.3, respectively). The same was true at the 2-month timepoint (mean residual AHI = 3.4; 3.2, 3.7 and 3.5, respectively). Mask leak was also well within normal limits at both the 2-month (mean = .14; .11, .15, and .16 lps) and 4-month timepoints (mean = 12; .12, .12, and .13 lps).

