Aim 3: To examine the effect of SM-Mobile, compared to UC and SM, on OSA apnea outcomes (e.g., OSA symptoms and OSA-specific health-related quality of life [HRQOL]). The Epworth Sleepiness Scale scores dropped from baseline to 2-months by 3.4 points and to 4-months by 4.0 points. Given that the cut-off for the ESS is 10 points (above which is considered sleepy; below which is considered within normal limits), all three interventions combined to reduce the sleepiness level of the sample from the sleepy range to the normal limits range (i.e., from mean ESS score of 11.8 to mean ESS score of 8.4 and 7.8 for 2-months and 4-months respectively). The mean ESS scores did not differ significantly between the groups at either the 2-month timepoint (8.3, 8.5, and 8.5 for the 3 groups respectively, UC, SM and SM-Mobile) or the 4-month timepoint (7.9, 7.4, and 8.2 for the 3 groups respectively, UC, SM and SM-Mobile). Sleep quality as measured by the Pittsburgh Sleep Quality Index was also significantly improved across all 3 groups from baseline (mean 11.9) to 2-months (2.8 points, mean 9.1) and to 4-months (2.9 points, mean 9.0). The mean PSQI scores did not differ significantly between the groups at either the 2-month timepoint (8.7, 9.4, and 9.5 for the 3 groups respectively, UC, SM and SM-Mobile) or the 4-month timepoint (8.5, 9.0, and 9.7 for the 3 groups respectively, UC, SM and SM-Mobile).

STATISTICAL ANALYSIS PLAN (SAP):

Data Analytic Plan. Preliminary analyses will begin with an examination of the distribution of variables to assess their characteristics (means, standard deviations, skewness, and kurtosis), to provide descriptive statistics of the study population, and to allow assessment of randomization. Continuous measures will be tested for normality and homogeneity of variance. Non-normally distributed variables will be transformed to meet the normal distribution assumption for linear statistical models.

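### Aim 1 asks how SM-Mobile compares with UC and SM, but the posted SAP specifies only a three-group test of adherence, with no SM-Mobile contrast or confidence interval

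*Combined protocol and SAP*

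**What the plan says.** The findings section words Aim 1 as the effect of the "SM-Mobile) intervention compared to Usual Care (UC) and Self-Management Care (SM) on level of CPAP adherence relative to Usual Care". The question is thus about one arm against each of two others, with UC as the reference.

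The SAP paragraph for Aim 1 has two analysis steps: "An ANOVA will be used to assess the CPAP adherence at post-intervention among the three groups", then "Followed will be an ANCOVA by including potential covariates". The general Data Analytic Plan says the same. The post-intervention point is not tied to a month. Four months is the natural reading, because enrolment lasted 4 months.

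The only remark bearing on individual comparisons is "An intent-to-treat analysis will be performed and no correction will be made for multiple comparisons". It names none.

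On repeated measures: "The outcomes in secondary aims 2 and 3 will also be assessed by the random effects model". The reason given is that "It accommodates unequal time intervals and will include all available data, minimizing the effects of missing data on the analyses". The Aim 2 and Aim 3 paragraphs present this model as a secondary analysis; the Aim 1 paragraph does not mention it.

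The findings report hours per night at 2 months (UC 4.0, SM 3.9, SM-Mobile 3.8; F = .113, p = .893) and at 4 months (3.6 in each arm; F = .041, p = .959). There is no pairwise difference, no interval and no group size.

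**The concern.** An omnibus F asks whether the three means differ at all. It does not estimate SM-Mobile minus UC or SM-Mobile minus SM, which are the quantities in Aim 1. When the result is null, what a reader most needs is how large a benefit or harm remains compatible with the data. A large p-value does not say that directly.

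A single-visit ANOVA also cannot use the 2-month hours of someone with no 4-month value. The SAP gives a reason for wanting a model that can, then applies it only to secondary outcomes. New CPAP users have no baseline adherence, so no change score exists, but two post-baseline visits are enough for a group-by-visit model.

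**Working it through.** **Inputs.** From the findings: means as above; SDs for UC, SM and SM-Mobile of 2.2, 2.4, 2.4 at 2 months and 2.2, 2.5, 2.5 at 4 months; the two F and p values. Not given: group sizes, target difference, loss to follow-up. Equal arms are assumed. The plan has no design figure to reproduce, so the check starts from the results.

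**1. What was tested.** With 2 numerator df and 60 to 300 denominator df, F = .113 gives p = .893. F = .041 gives p = .960, and .0415, which rounds up from the same figure, gives .9594. Both reported results are therefore 2-df omnibus tests.

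**2. Precision at 4 months.** With n per arm, F = n × var(means) / MSW, where MSW is the mean within-arm variance. So SE² of a pairwise difference = 2 × MSW / n = 2 × var(means) / F.
- Three means that all round to 3.6 lie within 0.1 h of each other, so var(means) is at most 0.1²/3 = 0.00333. F is at least .0405.
- SE is at most √(2 × 0.00333 / .0405) = 0.406 h. Times 1.97, the half-width is at most 0.80 h.
- The smallest MSW that the rounded SDs allow is (2.15² + 2 × 2.45²)/3 = 5.54, so n is at least .0405 × 5.54 / 0.00333, about 67 per arm.

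**3. Precision at 2 months.** Rounding lets var(means) be as small as 0.0025 (means 3.95, 3.90, 3.85).
- Smallest half-width: √(2 × 0.0025 / .1135) × 1.96 = 0.41 h. With MSW at most (2.25² + 2 × 2.45²)/3 = 5.69, this corresponds to n of at most .1135 × 5.69 / 0.0025 = 258 per arm.
- Largest half-width: taken alone, the 2-month figures allow about 1.3 h, but that needs only about 25 per arm, against at least 67 at 4 months. If the 2-month n is no smaller than the 4-month n, the limit is √(2 × 5.69 / 67) × 1.97 = 0.81 h.

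**4. What is excluded.** At 4 months SM-Mobile minus UC lies within 0.1 h of zero, so effects beyond about 0.1 + 0.80 = 0.9 h are excluded. If the 4-month n is no larger than 258, the half-width is at least √(2 × 5.54 / 258) × 1.96 = 0.41 h. A half-width between 0.41 and 0.80 h leaves open whether, for example, 0.5 h is excluded.

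**5. Loss to follow-up (all rates assumed).** Simulated hours had mean 3.9, SD 2.35 at 2 months and mean 3.6, SD 2.4 at 4 months before flooring at 0, with no true group difference and visit correlation 0.6 to 0.9. People under 2 h at 2 months lose the 4-month value at the rates shown.

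| Loss, UC vs SM-Mobile | Error in SM-Mobile minus UC, 4-month values only |
|---|---|
| 50% vs 20% | -0.13 to -0.20 h |
| 40% vs 20% | -0.09 to -0.13 h |
| 30% vs 20% | -0.04 to -0.06 h |
| 20% vs 50% | +0.13 to +0.20 h |
| equal | 0 |

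The random effects model stays within 0.01 h of zero. That is expected, since loss here depends only on observed 2-month hours. If instead lost people have stopped CPAP unrecorded (20% UC, 10% SM-Mobile), the true difference is +0.37 h and both analyses give about 0.

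**The case against.** Much can be said for the plan, and most of it stands.

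- **An omnibus F is ordinary for three arms.** True, and power is no argument against it. For a true 1.0 h at 67 per arm and SD 2.4, the F test has 56% against 67% for the contrast if SM lies midway, but 70% against 67% if SM equals either of the other arms. The gap is the missing estimate.
- **Pairwise comparisons may have been intended.** The multiple-comparisons remark suggests this, and the posted SAP may be an extract: its cost analysis "is fully described in section D.7 below", and that section is absent. So a reader should not infer that contrasts were ruled out or never computed. The posted text specifies none and the findings report none.
- **A reader might infer that the primary aim has a weaker main method than the secondary aims.** It does not. ANOVA and ANCOVA are the main analyses throughout. Aim 1 lacks one secondary analysis, described as useful for examining changes, and adherence has no change from baseline.
- **A reader might infer that the reported null is biased.** The documents give no loss figures. Every rate above is assumed, the error can go either way, and equal loss gives none. Hours may also come from device downloads that already record non-use as 0; the SAP does not say.
- **The results are not uninformative.** Step 4 shows that they exclude effects beyond about 0.9 h. But that takes back-calculation from rounded figures and an equal-arms assumption, which a reported interval would make unnecessary.

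**Conclusion.** The point holds and is worth fixing, but it does not overturn the trial. Aim 1 asks for SM-Mobile against UC and SM; the posted SAP specifies an omnibus test at one unnamed visit and no contrast or interval; and the results were reported in that form.

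Assuming equal arms, the unreported 4-month half-width is at most about 0.80 h. The 2-month half-width is about 0.4 to 0.8 h if no fewer people were analysed then. Leaving adherence out of the all-available-data model would cost about 0.04 to 0.20 h under assumed unequal loss among low users, and nothing under equal loss.

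Both visits were null with nearly equal means, so the reported conclusion is unlikely to change. The unnamed visit and the absence of a rule for scoring stopped or unrecorded use are missing detail, not evidence of error.

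**What to change.** Keep the planned ANOVA and ANCOVA. Add, at 4 months and in hours, SM-Mobile minus UC and then SM-Mobile minus SM, each with a 95% CI. Take them from the SAP's own random effects model extended to 2- and 4-month adherence by randomised group, with group, visit, group-by-visit and the planned covariates. Report numbers randomised and analysed per arm. If run now, label these analyses post hoc; they do not replace the reported primary test.

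Optionally, add a sensitivity analysis counting participants with no data as 0 hours, described as a bound. With 20% against 10% without data it would give +0.37 h even if the true difference were 0.

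The cost is a few lines of SAP text and an analysis of data already collected. The gain in precision is small: the SE falls by about 2 to 8% with 10 to 20% missing at 4 months and a visit correlation of 0.6 to 0.85. The model assumes missing at random, so it does not help if lost participants stopped CPAP unrecorded.

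A separate point to reconcile: the general plan admits a covariate if it meets either the imbalance or the association criterion, whereas the aim paragraphs require both.

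### The SAP gives two incompatible rules for choosing ANCOVA covariates ('or' in the general plan, 'and' plus an undefined clause under Aims 1 to 3) and does not say which prevails

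*Combined protocol and SAP*

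**What the plan says.** **General rule (SAP, Data Analytic Plan).** Four candidates are named: age, gender, education and baseline OSA severity. They "will be included as covariates in the ANCOVA model if found to be moderately associated ($p < 0.15$) with the outcome under study" "or unbalanced ($p < 0.10$) among intervention groups". Passing either screen is enough. Adjustment has two stated purposes: to correct baseline imbalance, and "to adjust for variables known to influence outcome independently of intervention".

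**Aim-level rule (SAP, Aims 1, 2 and 3, same sentence each time).** "Any variable that is significantly different at baseline ($p < 0.10$) and found to be associated with response ($p < 0.15" is included, so both screens must be passed. The sentence then adds clinically significant variables, with no list or definition.

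**Link between the two.** The general plan ends: "Given below are detailed analysis plans for the primary aim and secondary aims 1 and 2". It does not say that the detailed plans replace the general rule. The sections that follow are headed Aims 1 to 3, so even the labels do not match.

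**Role of the ANCOVA.** "The analytic model is based on an analysis of variance on the post-intervention measure (primary aim"; the same sentence goes on to apply the analysis of variance to the change measures of the secondary aims. For those measures "the ANOVA will be accompanied by an analysis of covariance (ANCOVA) on the change scores". Aim 1 opens with "An ANOVA will be used to assess the CPAP adherence at post-intervention among the three groups" and an ANCOVA follows. Under Aims 2 and 3 only the random effects model is labelled secondary. No aim names a deciding test.

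**The concern.** The two rules select different models from the same data. They differ most for a covariate that predicts outcome and is well balanced, which is what randomisation usually delivers: 'or' keeps it and 'and' drops it. Dropping it works against the second stated purpose of adjustment. The undefined clause could put it back, but leaves that choice to whoever runs the model.

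The conflict is live in this trial. Finding, Overall Sample, reports no significant group difference on AHI. If AHI is the severity measure and its p was 0.10 or more (the threshold used is not stated), 'and' excludes it, while 'or' includes it if it is associated with the outcome. No group comparison is given for age, gender or education. Finding, Aim 1, gives one F and one p per time point without naming the model or any covariates, so a reader cannot tell which rule, if either, was applied.

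**Working it through.** The documents give no sample size, power or effect size, so there is no design figure to reproduce. Steps 1 and 2 use only the SAP's thresholds. Step 3 rests on assumptions.

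**1. One covariate.** Randomisation makes the imbalance test a true null, so it is passed with probability .10. Let *a* be the chance of passing the association screen: .15 for an unrelated variable, near 1 for a clearly prognostic one. Treat the screens as independent.

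- 'And' admits with probability .10*a*.
- 'Or' admits with probability .10 + *a* − .10*a* = .10 + .90*a*.
- The rules disagree with probability .10 + .80*a*.

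| | 'and' | 'or' | disagree |
|---|---|---|---|
| unrelated (*a* = .15) | .015 | .235 | .22 |
| clearly prognostic (*a* = 1) | .10 | 1.00 | .90 |

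So 'and' omits any one prognostic covariate with probability at least 1 − .10 = 90%.

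**2. Four independent candidates.**

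- 'And' admits none: .985⁴ = 94% if none is associated; .90⁴ = 66% if all certainly are. In those trials, unless the undefined clause adds something, the Aim 1 ANCOVA merely repeats the ANOVA.
- The two rules select different sets: 1 − .78⁴ = 63% if none is associated; 1 − .10⁴ = 99.99% if all are.

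Simulation with the SAP's own screening tests agrees: sets differ in 61 to 100% of trials, and 'and' is empty in 65 to 94%.

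**3. Power (illustration).** *Arm size.* If the reported F values came from unadjusted equal-n ANOVAs, the 4-month result (F = .041, all means rounding to 3.6, smallest mean variance consistent with rounding (2.15² + 2.45² + 2.45²)/3 = 5.5425) needs n ≥ .0405 × 5.5425/.00333 = 67.3, so about 68. Using the reported p = .959 as well moves this to 69. The 2-month means allow up to 258.

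*Assumptions.* One arm shifted by 0.4 or 0.5 SD; joint R-squared of the four covariates 0 to .30 (for Aims 2 and 3, the share left after the baseline score); 2-df F test at 5%; 10,000 simulated trials per scenario. Entries are power, 'and' v fixed four-variable set.

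| per arm | shift | R² 0 | R² .05 | R² .18 | R² .30 |
|---|---|---|---|---|---|
| 68 | 0.5 SD | 86 v 86 | 86 v 87 | 86 v 91 | 87 v 95 |
| 68 | 0.4 SD | – | – | 67 v 75 | 67 v 81 |
| 80 | 0.5 SD | 91 v 91 | 91 v 92 | 92 v 95 | 92 v 98 |
| 80 | 0.4 SD | – | – | 74 v 82 | 76 v 88 |
| 120 | 0.4 SD | – | – | 91 v 95 | 91 v 97 |

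At 0.5 SD the 'or' rule tracks the fixed set (at 68: 86, 87, 91, 95%).

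*Check by noncentral F,* λ = n·d²·(2/3)/(1 − R²). At 68 per arm and 0.5 SD, λ = 68 × .25 × .6667 = 11.33 gives ANOVA power 85.8%. At 0.4 SD, λ = 7.25 gives 66.5%, and 7.25/.70 = 10.36 gives 82.4% for the fixed set at R² .30. The simulated values lie within about 1.5 points of these.

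**4. Type I error.** At 68 to 120 per arm, 'and' gave 4.0 to 5.3% and 'or' 4.7 to 5.4%.

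**The case against.** **The detailed text prevails.** Specific wording normally governs general wording, and the 'and' sentence appears identically under three aims. This lean is real. A reader might infer that any two analysts will usually fit different ANCOVAs; the documents do not support that. The 63% to nearly 100% holds only if one applies 'and' and the other 'or'. Two analysts who both follow the aim sections run the same screen, and only the undefined clause can separate them. But the SAP never withdraws the general rule, and the 'and' reading still leaves that clause open.

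**Prognostic variables can enter as clinically significant.** True, and it reduces the loss: if the clause admits the strongest covariate, the shortfall at 68 per arm and 0.5 SD falls to 2.5 points (R² .18) and 3.5 points (R² .30). It does so only through a choice the SAP does not define. Correcting imbalance is also a stated purpose, and 'and' serves it in part.

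**The ANOVA decides, so the ANCOVA rule hardly matters.** Much of this stands. A reader might infer that the conflict reaches the deciding test in Aims 2 and 3 but not in Aim 1. The full base-model sentence covers the secondary aims too, and ANOVA is listed first under every aim. The lean to ANOVA is common to all three, and so is the missing label.

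**The power figures are invented conditions.** They are assumptions and are shown as a range. The results in steps 1 and 2 do not need them.

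**Conclusion.** The contradiction is literal and should be fixed. Its firm size comes from the SAP's own thresholds, given randomised arms and independent screens and candidates: 'and' omits any one prognostic covariate about 90% of the time unless the undefined clause admits it, and 'and' and 'or' select different sets in 63% to nearly 100% of trials. The power cost of 'and' against a fixed set is conditional: about 0 to 14 points at about 68 per arm and 0 to 6 at 120, for assumed effects of 0.4 to 0.5 SD and R-squared 0 to .30. It is about 1 point or less when R-squared is .05 or lower (shown at 0.5 SD).

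The effect falls mainly on the adjusted analyses. Two stronger inferences are not supported. Neither rule alone materially inflates type I error. Nor is there ground to think that the reported adherence conclusions would change: p = .893 and p = .959 are far from any threshold.

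**What to change.** - Replace both p-value screens and the undefined clause with one rule for every aim: an ANCOVA on the set the SAP already lists (age, gender, education, and baseline OSA severity with its measure named), plus the baseline score for Aims 2 and 3.
- State for every aim that the ANOVA is the base test, as the general plan already leans, and that the ANCOVA is supportive.
- Results are already reported, so a rewritten SAP cannot prespecify anything for them. Keep them as reported, state which model and covariates produced each F and p under Finding, Aim 1, and label any fixed-covariate re-run post hoc.

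The cost is SAP wording and a sentence of disclosure; a re-run is optional and uses variables the SAP already lists. The statistical price is a few degrees of freedom, about 0 to 1 power point against the ANOVA if none of the four covariates is prognostic (at 68 per arm, 86.3 v 85.7% at 0.5 SD and 66.7 v 65.5% at 0.4 SD).
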